7.1.2 STANDARD OF CARE STUDY PROCEDURES

Radiographic Analysis:

Plain x-ray analysis: All subjects would have undergone a routine clinical x-ray analysis prior to Visit 1. This includes bilateral x-ray views of the knee joint using a standing a/p, synaflexer standardized flexion weight bearing p/a (Synarc®), Merchant views and weight bearing lateral views. Radiographs will be assessed to determine study eligibility as open growth plates are an exclusion criteria. Plain radiographs will be reviewed for radiographic progression of joint space narrowing or osteophyte formation using the Kellgren-Lawrence classification system as well as the Iwano classification for the patello-femoral joint.

Previous studies have shown that that joint space narrowing measured on a standardized synaflexor platform has a high reproducibility and accuracy. At 2 years koint space narrowing has been identified in an ACL injured cohort using this system (32).

7.2 LABORATORY PROCEDURES/EVALUATIONS

7.2.1 CLINICAL LABORATORY EVALUATIONS

Clinical Laboratory Evaluations: none

Pregnancy test: Female participants of child bearing potential will have a urine pregnancy test at Visit 1. Pregnancy testing results must be negative in order for enrollment into the study.

Procedure for minors: A female minor is identified as a potential candidate for the study. The investigator or approved study staff approach the patient and accompanying parent/guardian to inform them that the patient may qualify for a study. Both parties are informed of the study. If interested in participating in the study, each research team will perform a pregnancy test for inclusion/exclusion in correspondence with their locally approved minor pregnancy testing protocol.

Non-Clinical Laboratory Evaluations:

Sample collection including joint arthrocentesis. Synovial fluid will be aspirated and spun at 3500 RPM for 10 minutes and the supernatant will be frozen at -70°C. Joint aspiration will be performed aseptically with local anesthesia through a superolateral suprapatellar approach. The aspiration syringe will be gently removed and the study drug/placebo-containing syringe will be attached, followed by injection. The supernatants will be stored, pending analysis, in the UK Center for Clinical and Translational Science Bioanalysis Lab. All biomarker analyses in synovial fluid, serum, and urine will be performed by co-Investigator [name] at Duke University.

IL-1β, IL-1α, IL-6 and IL-1Ra analyses - These cytokines will be measured in the synovial fluid using the high-sensitivity Quantikine (sandwich) Immunoassays (R&D). As described previously (39), the standard curve will be extended in the low range for the IL-1 α assay to further improve the specificity as we have found the standard curve of the assay to be reproducible and linear below the lower standard described in the procedural literature accompanying the reagents.

Glycosaminoglycan (GAG) - The S-GAG content, a marker of proteoglycan degradation, will be measured in synovial fluid with the dimethyl methylene blue dye (DMMB) assay as noted previously (40). Chondroitin sulfate from shark cartilage will be used as a standard between 5 and 50 mg/ml.

7.2.2 OTHER ASSAYS OR PROCEDURES

None

7.2.3 SPECIMEN PREPARATION, HANDLING, AND STORAGE

Refer to the study lab processing manual

7.2.4 SPECIMEN SHIPMENT

Refer to the study lab processing manual

7.3 STUDY SCHEDULE

7.3.1 SCREENING/ENROLLMENT

Visit 1 Screening 1-28 days following injury)

- Obtain informed consent and assent, if necessary, of potential subjects
- Review medical history to determine eligibility based on inclusion/exclusion criteria.
- Review medication history to determine eligibility based on inclusion/exclusion criteria.
- Perform medical examinations and collect vital signs as needed to determine eligibility based on inclusion/exclusion criteria. All subjects must have a clinical exam that is consistent with an ACL tear.
- Collection of urine and blood for laboratory testing. Women of child bearing potential will be given a urine pregnancy test. Test must be negative in order to enroll into the study.
- Subjects will have the following assessments: range of motion, knee instability (Lachman's test) and standardized MTP-2 weight bearing x-rays.
- Standard questionnaires including the KOOS, IKDC, VR-12 and a Likert pain scale.
- Research knee MRI

Following the review of above assessment results and a review of inclusion/eclusion criteria, subjects will be randomized into 1 of 3 treatment groups. Following randomizing, subjects will undergo a knee aspiration and will receive their first dose study medication.

Visit 2 (day of surgery or 4-6 weeks post injury)

- Knee aspiration (in the operating room under anesthesia)
- Patient reported outcomes (PROs) administered prior to surgery
- KOOS, IKDC, VR-12 and a Likert pain scale administered prior to surgery
- Biomarkers (urine and blood) pre-operatively
- Review for AE's and SAE's
- ROM will be performed prior to surgery

Visit 3 (4-14 days After Visit 2)

- Knee aspiration (if clinically indicated)
- Biomarkers (urine and blood)
- Review for AE's and SAE's
- ROM will be performed

Visit 4 (6 month After Visit 2+/- 2 weeks)

- Patient reported outcomes (PROs) administered
- KOOS, IKDC, VR-12 and a Likert pain scale administered
- Review for AE's and SAE's

• ROM will be performed

Visit 5 (12 monthsAfter Visit 2+/- 2 weeks)

- ÀRI
- Patient reported outcomes (PROs) administered
- KOOS, IKDC, VR-12 and a Likert pain scale administered
- Biomarkers (serum and urine only)
- Review for AE's and SAE's
- ROM will be performed

Visit 6 (24 month After Visit 2+/- 2 weeks)

- MRI
- Patient reported outcomes (PROs) administered
- KOOS, IKDC, VR-12 and a Likert pain scale administered
- Biomarkers (serum and urine only)
- Review for ÀE's and SAE's
- ROM will be performed

7.3.2 SCHEDULE OF EVENTS TABLE

This section should capture the procedures that will be accomplished at each study visit and correspond to the descriptions in the above sections.

Procedures	Screening (Visit 1)	Visit 2 ^e	Visit 3	Visit 4	Visit 5	End of Study Visit 6
Time point	1-28 days post injury	Surgery day or 4-6 weeks post injury	4-14 After Visit 2	6 months After Visit 2 (+/- 2 weeks)	12 After Visit 2 (+/- 2 weeks)	24 months After Visit 2 (+/- 4 weeks)
Informed Consent	Х					
Demographics	Х					
Medical history	Х	Х	Х	Х	Х	Х
Randomization	Х					
Administer Investigational Product	Х					
Concurrent meds	Х	Х	Х	Х	Х	Х
Physical Exam	Х					
Range of motion	Х	Х	Х	Х	Х	Х
Vital signs	Х					
Height	Х					
Weight	Х					
Questionnaires	Х	Х		Х	Х	X
Knee Aspiration	Х	Xa	X ^h			
Biomarkers	Х	Х	Х		X ^d	X ^d
Safety Lab Tests ^b	Х					

Procedures	Screening (Visit 1)	Visit 2 ^e	Visit 3	Visit 4	Visit 5	End of Study Visit 6	
Urine pregnancy tests ^c	Х						
Adverse event evaluation	Х	Х	Х	Х	Х	Х	
X-Ray ^f	Х						
MRI ^g	Х				Х	Х	
a: Should a subject be enrolled into the study and choose not to undergo ACL reconstruction aspiration at time of surgery will be omitted. b: Albumin, alkaline phosphatase, total bilirubin, bicarbonate, BUN, calcium, chloride, creatinine, glucose, LDH, phosphorus, potassium, total protein, SGOT [AST], SGPT [ALT], sodium. c: Urine pregnancy test (women of childbearing potential). d: Serum and urine only e. Should a subject be enrolled into the study and choose not to undergo ACL reconstruction, subject will received treatment according to this protocol. For subjects that do not have ACL reconstruction, the time windows will be relative to Visit 2. For example, Visit 3 will be 4-14 days after Visit 2 f. All subjects must have standardized MTP-2 weight bearing x-ray. Documentation of closed growth plates at screening will be noted in the routine SOC x-ray							

g. All subjects enrolled will have an MRI performed regardless if surgery is to be scheduled or not. However, randomization can be performed prior to MRI as the MRI examination is not necessary or required to diagnose the ACL tear.
h. We will only perform the aspiration at Visit 3 if participants had elected to have surgery performed, and if they have fluid on their

knee.

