2 INTRODUCTION: BACKGROUND INFORMATION AND SCIENTIFIC RATIONALE

2.1 BACKGROUND INFORMATION

A majority of individuals with partial or complete rupture of the anterior cruciate ligament (ACL) develop post-traumatic osteoarthritis (PTOA) 5-15 years after the initial injury. The long-term consequences of PTOA include arthrofibrosis, pain, limited motion, and recurrent instability. Because ACL injuries occur most often in younger individuals (average age 14-29 years), pain and other debilitating symptoms occur most often during patients' most productive years costing society upwards of 3.06 billion dollars annually [1]. Current surgical and non-surgical treatment options for ACL injury, while relatively successful in restoring function and stability in the short term, do little or nothing to reduce or prevent the development of PTOA later in life.

ACL rupture, with or without accompanying damage to nearby cartilage and bone, initiates a persistent cascade of inflammation and catabolic enzyme activity leading to OA of the knee joint. We propose to disrupt the inflammation-driven cascade with recombinant Interleukin 1 receptor antagonist (IL-1ra).

IL-1ra was chosen because it is safe, well tolerated, and has been used to treat RA, juvenile inflammatory arthritis, and post-surgical persistent knee effusions as well as knee stiffness.[2-4_] Our own preliminary data suggests that IL-1ra reduces pain and improves function in patients with acute knee injury and arthrofibrosis. IL-1ra binds to the Interleukin 1 receptor and nonproductively blocks the proinflammatory and cartilage catabolic activities of Interleukin 1 alpha and beta. IL-1ra levels in synovial fluid are initially higher following acute ACL injury but vanish rather quickly. Subsequently, IL-1 β levels rise slower in joint fluid after ACL rupture and remain high for longer periods of time. IL-1ra has had mixed results in the treatment of established OA, possibly due to its short half-life in vivo. However, if given shortly after the initial inciting event potentially initiating the development of OA, the effectiveness may be significantly higher.

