Study 1: *IL-1Ra decreased pain in an open label trial of arthrofibrosis:* [name], Co-Investigator of this study, conducted two small clinical trials to test the beneficial effect of IL-1ra, an inhibitor of IL-1 biological activity, in vivo. Six patients who failed to meet entry criteria for a separate randomized trial because of age or time from injury to presentation, were entered into a small open label study in which they received 150 mg IL-1ra (anakinra, Amgen) intraarticularly for the treatment of acute ACL injury (n=2), or chronic, recurrent, arthrofibrosis following surgical lysis of adhesions (n=4). All 4 arthrofibrosis patients reported improvement in knee pain, swelling, and joint motion. Examination by the treating physician and by physician global assessment confirmed these results. Five out of six patients reported clinically significant pain relief after the treatment. There were no other complaints related to the drug and no evidence of significant adverse events in any patient. These results corroborate findings from animal studies and imply that adequate exposure to IL-1Ra early in the course of disease may potentially reduce pain and stiffness (21).

Study 2: IL-1Ra decreased pain, and improved function, and lowered IL-1 α levels in synovial fluid in a randomized pilot trial of ACL rupture: In a second randomized trial, 11 patients with isolated ACL tears scheduled for later ACL surgery were treated with 150 mg (anakinra, Amgen; 6 patients) or equal volume saline placebo (5 patients) intra-articularly within the first 30 days of acute knee injury. Mean age of participants was 24 ± 4 (SD) years, (6 male, 5 female). Enrollment was limited to patients under 40 years of age to try to insure the lack of underlying pre-existing arthropathy. Patients were recruited a mean 15 ± 7 (SD) days from injury (range 6-27 days). Self-report of pain on a Likert scale 0-10 was recorded at baseline (0), 4 days, 14 days, and 28 days after treatment as well as on the day of surgery. The standardized KOOS and IKDC questionnaires were also obtained.

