10 STATISTICAL CONSIDERATIONS

10.1 STATISTICAL AND ANALYTICAL PLANS

10.1.1 GENERAL APPROACH

Sample Size and Power Analysis - The primary outcome aim of the study is to determine if treatment with the study medication results in greater improvements in patient-reported outcomes one year following surgery. We will use the validated Knee Osteoarthritis and injury Outcome Score (KOOS),[27] which is a self-administered, knee-specific instrument that evaluates the course of knee injury and treatment outcomes. To reduce the risk of an underpowered RCT, an a priori sample size estimation was calculated from data collected from recent studies of ACL-injured and -reconstructed patients.[28-32] The previously published oneyear KOOS Quality of Life Scores are 60.2 ± 24.2 [31] and the minimal detectable change of this instrument is 7.2 [32]. Assuming that the standard deviation of the change scores between the day of surgery and one year postoperative visits will be 20% of the standard deviation of the standard deviation of the one-year KOOS Quality of Life Scores ($.2 \times 24.2 = 4.8$), a sample size of 16 patients per group (32total) would be at least 80% powered to detect a difference of 7.2 points between the treatment group and the control group (One-way ANOVA model with alpha = 0.05, Effect size = 7.2/4.8 = 1.5, G*Power 3.0.10). This sample size would adequately power the study for the primary outcome variable, but would also adequately power the study for the second aim of the study. The second aim of the study is to compare chondrodegenerative biomarkers between groups at the 1 year follow up. We have previously observed large effect sizes between groups in preliminary studies (ES = 1.34), and a sample size of 32 patients (16 per group) would be at least 80% powered to detect effect sizes of this magnitude. However, to protect against an underpowered study due to patient attrition, we will monitor compliance and potentially enroll up to 20 patients per group in order to adjust for attrition. Patient costs will not occur until sample or MRI analysis.

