10.2 MEASURES TO MINIMIZE BIAS

10.2.1 ENROLLMENT/ RANDOMIZATION/ MASKING PROCEDURES

Randomization: Following informed consent and after successfully being screened into the study, subjects will be randomized to one of three treatment groups.

- **Group 1** will receive intra-articular injection of Anakinra (Kineret®, IL-1ra; 150mg) 1-28 days after ACL injury.
- **Group 2** will receive intra-articular injection of saline placebo 1-28 days after ACL injury.

Blinding: To ensure triple-blindness, an uninvolved third party will generate the allocation sequence of the intervention and provide this to the principal investigator. Allocation of drug or placebo will be by permutated random block size, ensuring that approximately equal numbers of subjects will be treated with drug or placebo in the unlikely event that the study will need to be terminated prematurely.

If subject discontinues the study for any reason prior to 3-month visit, then the collected data will be evaluated but not included in the analysis and a replacement subject will be enrolled in the study.

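### Time from injury to injection (1-28 days) enters neither the allocation nor any planned analysis, which may cost precision, chiefly for the Visit 2 biomarker endpoint

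*Combined protocol and SAP*

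**What the plan says.** In the combined protocol and SAP, the Schedule of Events Table (Section 7.3.2) places Visit 1, with randomisation and injection, at "1-28 days post injury". Visit 2 is at "Surgery day or 4-6 weeks post injury". A footnote adds: "For subjects that do not have ACL reconstruction, the time windows will be relative to Visit 2".

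Section 4.2.2 lists biomarkers in synovial fluid, serum and urine at surgery as a secondary endpoint. The primary endpoint (Section 4.2.1) is KOOS-Symptoms.

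On allocation, Section 10.2.1 says: "Allocation of drug or placebo will be by permutated random block size". It names no stratification factor.

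Section 10.1.1 plans a Friedman test for KOOS and a Wilcoxon signed-rank test with Hochberg correction for synovial fluid, or repeated measures ANOVA if normality holds. No covariate is named. Section 10.1.2 contains safety text only, and Section 10.1.3 is marked not applicable.

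On the biology, Section 2.1 states: "IL-1ra levels in synovial fluid are initially higher following acute ACL injury but vanish rather quickly". It adds that IL-1β rises more slowly and stays high for longer. Section 7.2.1 reports that CTX-II and xanthine oxidase rise in the first month after injury.

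**The concern.** A patient sampled a few days after injury and one sampled four weeks after are at different points on a marker curve that the protocol describes as moving. If that difference carries through to Visit 2, it sits in the error term of the biomarker comparison. Randomisation balances it only on average, and with 16 to 20 patients per arm a single trial can end with visibly different mean times.

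The value is known at Visit 1 and needed for eligibility, so leaving it out is a choice of analysis, not a limit of the data. The Précis also names timing of administration as something the study aims to establish, but no analysis uses it. Without a pre-specified rule, whether to adjust would be decided after any imbalance is seen.

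**Working it through.** **The plan's own figure.** Section 10.1.1 states that "a sample size of 16 patients per group (32total) would be at least 80% powered to detect a difference of 7.2 points", with effect size 7.2/4.8 = 1.5 and two-sided alpha 0.05. An exact two-sample t calculation gives 98.4% power at 16 per group; 80% would need 9. So the statement holds as a lower bound. It concerns one-year KOOS Quality of Life. The biomarker statement beside it (effect size 1.34, 95.6% power at 16 per group) also concerns one year. Neither covers Visit 2 biomarkers.

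**Delay from injection to Visit 2.** For the 4-6 week alternative (days 28 to 42), the shortest delay is 28 − 28 = 0 days and the longest 42 − 1 = 41 days. The surgery-day alternative has no stated limit. In the group's earlier trial (Section 2.1, Table 1) surgery fell at 10-51; if the unit is days, which the table does not say, a delay of 51 − 1 = 50 days is possible.

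**Chance imbalance in mean days since injury.** The 95% half-width is 1.96 × SD × √(2/n). The documents offer three readings of the SD:
- Pilot trial (Section 2.1, Study 2): "Patients were recruited a mean 15 ± 7 (SD) days from injury (range 6-27 days". SD = 7.
- Uniform spread over days 1-28: SD = √((28² − 1)/12) = 8.08.
- Earlier trial (Table 1): range 1-8, mean 4.17. On those figures the SD cannot exceed √((8 − 4.17)(4.17 − 1)) = √(3.83 × 3.17) = 3.48.

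| SD (days) | 16 per arm | 20 per arm |
|---|---|---|
| 7 | ±4.9 | ±4.3 |
| 8.08 | ±5.6 | ±5.0 |
| 3.48 (upper bound) | ±2.4 | ±2.2 |

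In SD units the standard error is √(2/16) = 0.354, so the chance of an imbalance above 0.5 SD is 16% at 16 per arm (11% at 20). At the 95% limit of 1.96 × 0.354 = 0.69 SD, the unadjusted difference shifts by r × 0.69 outcome SDs: 0.21 at r = 0.3 and 0.35 at r = 0.5.

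**Effect of adjusting.** The variance with one covariate, relative to the unadjusted comparison, is (1 − r²)(1 + 1/(2n − 4)). The correlation r is not in the documents, so a range is shown.

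| r (assumed) | 16 per arm | 20 per arm |
|---|---|---|
| 0 | 1.036 | 1.028 |
| 0.2 | 0.994 | 0.987 |
| 0.3 | 0.943 | 0.935 |
| 0.5 | 0.777 | 0.771 |

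At 16 per arm, r = 0.3 is worth 16/0.943 = 17.0 patients per arm and r = 0.5 is worth 16/0.777 = 20.6. If the Visit 1 biomarker value is also in the model, r means the correlation left after that value and may be smaller.

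**Type I error and power.** In simulations of 20,000 trials per setting with timing uniform on days 1-28, the unadjusted test rejected a true null in 4.7-5.1% of trials. At 16 per arm and a true effect of 1.0 SD, adjustment raised power from 79% to 81% (r = 0.3) and from 78% to 87% (r = 0.5). At the plan's effect size of 1.5 it added at most about one point.

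**The case against.** The strongest reply is that nothing in the documents ties days since injury to any KOOS score. Sections 2.1 and 7.2.1 speak of markers, and the primary endpoint is a symptom score. That stands: a reader might infer that timing is prognostic for symptoms too, but the documents do not show it, and r near zero cannot be excluded.

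The size is also uncertain. A reader might assume that timing explains 10-30% of variance and compute 1/(1 − R²) − 1 = 11% to 43% more patients. That omits the lost degree of freedom: at 16 per arm, 1/(0.9 × 1.036) and 1/(0.7 × 1.036) give about 7% to 38%. It also omits the small correlations at which there is no gain. The pilot SD comes from 11 patients, while the earlier trial, described as having identical enrolment criteria, points to half the imbalance or less. The present 1-28 day window permits more spread than that trial saw, so both figures belong in the range.

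Finally, Friedman and signed-rank tests take no covariate, so adjustment means naming a different model. That stands and is part of the fix. So does the warning about the delay from injection to Visit 2: it arises after randomisation, treatment could affect it through recovery and surgery timing, and conditioning on it could bias the comparison.

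**Conclusion.** The point holds for the Visit 2 biomarkers: a baseline variable that the protocol describes as tracking marker change is left out of both allocation and analysis. The expected imbalance is about ±4.9 days at 16 per arm with the pilot SD, or at most ±2.4 if enrolment is as early as in the previous trial. The effect of adjustment on variance runs from a 4% loss (r = 0) to a 22% saving (r = 0.5), with r assumed throughout.

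Two stronger readings are not supported. The omission does not bias the comparison systematically or inflate overall type I error; it is random error that could be reduced. Nor is 41 days the maximum delay to Visit 2, since that figure applies only to the 4-6 week alternative. For KOOS, the case for adjusting is an assumption.

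**What to change.** Leave the schedule and allocation as they are. For the Visit 2 biomarker endpoint, replace the signed-rank comparison with a between-group ANCOVA or mixed model, on log or rank-transformed values if needed. Pre-specify two covariates: the Visit 1 biomarker value, taken before injection, and days from injury to injection. The same timing covariate may be added to a KOOS model as a secondary analysis.

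Report days from injection to Visit 2 by arm, and label any model that includes that delay as supportive only. For visits in the 4-6 week window the delay and the time to injection sum to 28-42 days, so their effects will be hard to separate.

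The timing covariate costs one degree of freedom and about 4% of variance at 16 per arm if timing is not prognostic. The SAP must also name a covariate model in place of the rank tests, which is more than a one-line edit. No new data are needed beyond the dates of injury, injection and Visit 2.

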7.4 JUSTIFICATION FOR SENSITIVE PROCEDURES

Not Applicable.

7.5 CONCOMITANT MEDICATIONS, TREATMENTS, AND PROCEDURES

All concomitant prescription medications taken during study participation will be recorded on the case report forms (CRFs). For this protocol, a prescription medication is defined as a medication that can be prescribed only by a properly authorized/licensed clinician. Medications to be reported in the CRF are concomitant prescription medications, over-the-counter medications and non-prescription medications including herbal supplements.

